2.4.5.3 Deaths

The following deaths summaries will be generated on the safety population, during the main 6-month on-treatment period and for the 12-month on-treatment period separately:

• Number (%) of patients who died by study period (on-study, on-treatment, post-study) and reasons for death;

- All TEAEs leading to death (death as an outcome on the adverse event e-CRF page as reported by the investigator), by primary SOC, HLGT, HLT, and PT, showing number (%) of patients sorted by SOC internationally agreed order. The other levels (HLGT, HLT, PT) will be presented in an alphabetic order;
- A listing of all deaths.

2.4.5.4 Analyses of laboratory variables

The summary statistics (including number, mean, median, standard deviation, minimum, and maximum) of all laboratory variables (central laboratory values and changes from baseline) will be calculated for each visit or study assessment (baseline, each post-baseline time-point, last on-treatment value during the main 6-month and 12-month on-treatment periods) by treatment group. This section will be organized by biological function as specified in Section 2.1.4.4.

The incidence of PCSAs (list provided in Appendix C) at any time during the main 6-month on-treatment period and during the 12-month on-treatment period will be summarized by biological function and treatment group whatever the baseline level and according to the following baseline status categories:

- Normal/missing,
- Abnormal according to PCSA criterion or criteria.

For parameters for which no PCSA criteria are defined, similar table(s) using the normal range will be provided.

Drug-induced liver injury

The liver function tests, namely AST, ALT, ALP, and total bilirubin, are used to assess possible drug-induced liver toxicity. The proportion of patients with PCSA values at any post-baseline visit by baseline status will be displayed by treatment group for each parameter.

A graph of distribution of peak values of ALT versus peak values of total bilirubin will also be presented. Note that the ALT and total bilirubin values are presented on a logarithmic scale. The graph will be divided into 4 quadrants with a vertical line corresponding to 3 x upper limit of normal (ULN) for ALT and a horizontal line corresponding to 2 x ULN for total bilirubin.

Listing of possible Hy's law cases will be identified and provided by treatment group (eg, patients with any elevated ALT>3 x ULN, and associated with an increase in bilirubin >2 x ULN) with ALT, AST, ALP, total bilirubin, and the following complementary parameters (if available): conjugated bilirubin and prothrombin time / international normalized ratio (INR), CPK, serum creatinine, complete blood count.

The incidence of liver-related TEAEs will be summarized by treatment group. The selection of PTs will be based on the "Hepatic disorder" SMQ.

2.4.5.5 Analyses of vital sign variables

The summary statistics (including number, mean, median, standard deviation, minimum, and maximum) of all vital signs variables (raw values and changes from baseline) described in Section 2.1.4.5 including body weight, will be calculated for each visit or study assessment (baseline, each post-baseline time-point, last on-treatment during the main 6-month and 12-month on-treatment periods) by treatment group.

The incidence of PCSAs at any time during the main 6-month on-treatment period and during the 12-month on-treatment period will be separately summarized by treatment group whatever the baseline level.

2.4.5.6 Analyses of electrocardiogram variables

Not applicable.

2.4.5.7 Analyses of anti-insulin antibody data

The analyses of immunogenicity data will be descriptive (no formal statistical testing) and based on the AIA population. Separate analyses will be performed for the T1DM and T2DM patients. Analyses will be presented separately for the main 6-month and the 12-month on-treatment periods.

For T1DM patients, all analyses of immunogenicity will be produced except for analyses by subgroups defined by baseline and screening factors. Analyses by type of comparator (NovoLog, NovoRapid) will be produced.

For T2DM patients, the following analyses will be produced:

- Summary of AIA response,
- Summary of AIAs by visit,
- Summary of AIA response by prior NovoLog/NovoRapid (Yes, No),
- Summary of change in HbA1c (%) from baseline to Week 26 by treatment-emergent AIA,
- Summary of change in insulin dose (mealtime, basal, total daily) from baseline to Week 26 by treatment-emergent AIA,
- Scatterplot analyses to assess the relationship between immunogenicity endpoints and efficacy/safety assessments,
- Boxplots of maximal AIA titer.

Anti-insulin antibody response

The number and percentage of patients will be provided by treatment group for each of the following categories:

- Patients with treatment-induced AIAs,
- Patients with treatment-boosted AIAs,
- Patients with treatment-emergent AIA (AIA incidence),
- Patients without treatment-emergent AIA,
- Patients with pre-existing AIAs or treatment-induced AIAs (AIA prevalence).

For exploratory purposes, the difference between SAR341402 and NovoLog/NovoRapid in the percentage of patients with treatment-emergent AIAs (AIA incidence) will be provided with associated 2-sided 90% CI. Patients with inconclusive results will not be part of the analysis. Results will be obtained by fitting a binomial regression model with an identity-link function. The model will include fixed categorical effects for treatment, the randomization strata of geographical region and type of diabetes (Europe T1DM, US T1DM, US T2DM, Japan T1DM), screening HbA1c (<8%, \geq 8%), and prior use of NovoLog/NovoRapid (Yes, No). The risks within each treatment group and risk difference will be provided with their 90% CIs using the adjusted LS mean estimates of the treatment effect.

For patients with treatment-induced and treatment-boosted AIAs, the kinetics of AIA response (transient, persistent, or indeterminate AIA response as defined in Section 2.1.4.7) will be further summarized using number and percentage of patients, and the peak titer will be described using median, Q1 and Q3.

Incidence of patients with treatment emergent AIA will be compared, for SAR341402 versus NovoLog/NovoRapid using a logistic regression method. The model will include fixed-effect terms for treatment group, the randomization strata of geographical region and type of diabetes (Europe T1DM, US T1DM, US T2DM, Japan T1DM), screening HbA1c (<8%, \geq 8%), and prior use of NovoLog/NovoRapid (Yes, No). If the logistic model does not converge (e.g., due to sparse data), randomization strata may be removed from the model. Odds-ratios and 95% CIs will be displayed using forest plots.

The number and percentage of patients with treatment-induced, treatment-boosted and treatment-emergent AIAs will also be presented by visit in each treatment group using tables and/or graphs.

Boxplots of the peak AIA titer will be presented by treatment group and according to the treatment-emergent AIA status (Yes, No). These graphs will be used to identify AIA 'outliers', defined as peak AIA titers higher than the boxplot upper whiskers (ie, higher than 1.5 times the interquartile range above the third quartile).

Anti-insulin antibody data by visit

The number and percentage of patients with anti-SAR341402/NovoLog/NovoRapid antibody positive and antibody negative samples will be summarized by treatment group at each visit and at the last on-treatment value. The number and percentage of patients with anti-SAR341402/NovoLog/NovoRapid antibody positive sample will be displayed graphically by visit.

On the group of patients with anti-SAR341402/NovoLog/NovoRapid antibody positive sample at a given visit, anti-SAR341402/NovoLog/NovoRapid antibody titers will be summarized (using descriptive statistics by number (N), median, Q1, Q3, variation coefficient, minimum, maximum, geometric mean, SD, and 95% CI), and the number and percentage of patients with cross-reactivity to human insulin will be provided.

Boxplots of AIA titers will be presented at each visit.

The above by-visit summaries will be performed on the overall AIA population and separately for patients with treatment-induced, treatment-boosted and treatment-emergent AIAs.

Subgroup analyses

Exploratory analyses will be performed by subgroups defined by baseline and screening factors.

The following subgroups will be displayed:

- Race (American Indian or Alaska Native, Asian, Black or African American, Native Hawaiian or Other Pacific Islander, White, More than One Race, Unknown or Not Reported),
- Ethnicity (Hispanic or Latino, Not Hispanic or Latino, Unknown /Not Reported),
- Age group (<65, \geq 65 to <75, \geq 75 years of age),
- Sex (male, female),
- Baseline BMI (<30, ≥ 30 kg/m²),
- Baseline estimated GFR categories ($<60, \ge 60 \text{ mL/min}/1.73 \text{ m}^2$),
- Randomization stratum of type of diabetes (T1DM, T2DM),
- Randomization stratum of screening HbA1c (<8%, $\geq8\%$),
- Randomization stratum of prior use of NovoLog/NovoRapid (Yes, No),
- Type of comparator (NovoLog, NovoRapid),
- Regions (North America, Western Europe, Eastern Europe, ROW),
- Duration of diabetes ($<10, \ge 10$ years),
- Anti-SAR341402/NovoLog/NovoRapid antibody status at baseline (Positive, Negative).

Further subgroup analyses may be performed if deemed necessary for interpretation of results.

Relationship between immunogenicity endpoints and efficacy/safety assessments

Subgroup analyses and scatterplots will be conducted to assess the relationship between immunogenicity endpoints and efficacy/safety assessments.

The following efficacy/safety assessments will be summarized by treatment-emergent AIA (Yes, No) and treatment-emergent AIA at last on-treatment value (Yes, No):

- Primary efficacy endpoint (change in HbA1c from baseline to Week 26) (for the main 6-month analyses) and change in HbA1c from baseline to Week 52 (for the 12-month analyses): same statistical model as described in Section 2.4.4.1.4 for subgroup analyses will be performed.
- Hypoglycemia (any, severe, documented symptomatic): the proportion of patients with at least one event will be compared between treatment groups using the same statistical model as described in Section 2.4.5.1 for hypoglycemia subgroup analyses. The number of severe hypoglycemia and the number of documented symptomatic hypoglycemia <3.0 mmol/L (54 mg/dL) per patient will also be displayed for each treatment group.
- Common TEAEs: descriptive statistics by primary SOC, HLT, and PT, showing number (%) of patients sorted by SOC internationally agreed order. The other levels (HLT, PT) will be presented in an alphabetic order.
- Serious TEAEs: descriptive statistics by primary SOC, HLGT, HLT, and PT, showing number (%) of patients sorted by SOC internationally agreed order. The other levels (HLGT, HLT and PT) will be presented in an alphabetic order.
- Injection site and hypersensitivity reactions: descriptive statistics by PT, showing number (%) of patients sorted by decreasing incidence of PT in the SAR341402 group.
- Change in daily insulin doses (basal, mealtime, total) as defined in Section 2.4.3.1.

In order to assess the impact of pre-existing antibodies that may cross-react with SAR341402, the above parameters will also be summarized by AIA status at baseline (Positive, Negative).

The relationship between the AIA titer and the efficacy and safety assessments will be explored using scatter-plots of the peak AIA titer versus the parameters below for patients from the AIA population with titer available:

- Primary efficacy endpoint (change in HbA1c from baseline to Week 26) (for the main 6-month analyses) and change in HbA1c from baseline to Week 52 (for the 12-month analyses)
- Change in total insulin dose (U/kg) from baseline to Week 26 (for the main 6-month analyses) and to Week 52 (for the 12-month analyses)
- Rate per year of treatment-emergent hypoglycemia during the on-treatment period (severe hypoglycemia, documented symptomatic < 3.0 mol/L [54 mg/dL])
- Presence/absence of treatment-emergent hypersensitivity reactions during the on-treatment period

• Presence/absence of treatment-emergent injections site reactions during the on-treatment period

The scatterplots will also be presented separately for patients with treatment-emergent AIAs.

Listings of baseline characteristics, insulin doses, HbA1c, hypoglycemia, hypersensitivity reactions, and injection site reactions will be provided for patients with treatment-emergent AIAs and high AIA titers (AIA 'outliers' as defined above).

Additionally, descriptive statistics by categories of HbA1c change from baseline to Week 26 (for the main 6-month analyses) or Week 52 (for the 12-month analyses) (<-1%, \geq -1 to \leq 1\%, >1%) will be performed on the number (%) of patients with or without treatment-emergent AIA and associated peak titer, and on insulin doses (basal, mealtime, total). Listings of anti-insulin antibody, insulin doses, and HbA1c data will be provided for patients with treatment-emergent AIAs and HbA1c change from baseline > 1% at Week 26 (for the 6-month analyses) or Week 52 (for the 12-month analyses).

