1.3 DETERMINATION OF SAMPLE SIZE

The sample size calculation was performed based on the primary endpoint, change in HbA1c (%) from baseline to Week 26.

A sample size of 580 patients (290 patients per arm; approximately 480 T1DM patients [230 patients in the US using NovoLog and 250 patients in countries using NovoRapid] and 100 T2DM patients [all in the US using NovoLog]) will ensure that the upper bound of the 2-sided 95% confidence interval (CI) for the adjusted mean difference between SAR341402 and NovoLog/NovoRapid would not exceed a non-inferiority margin of 0.3% HbA1c with at least 95% power. This sample size will also ensure that the lower bound of this 2-sided 95% CI would not be below -0.3% HbA1c with at least 95% power, thus will provide at least 90% power to show both non-inferiority of SAR341402 over NovoLog/NovoRapid (primary analysis) and inverse non-inferiority of NovoLog/NovoRapid over SAR341402 (secondary analysis).

These calculations assume a common standard deviation (SD) of 1.0% and a true difference in HbA1c between the treatment groups of zero.

The non-inferiority margin of 0.3% HbA1c for the adjusted mean difference between SAR341402 and NovoLog/NovoRapid was chosen, as it is in line with recommendations by regulatory agencies including FDA, referring to a range of 0.3% to 0.4% (1), and the European Medicines Agency, suggesting the more stringent non-inferiority margin of 0.3% (2), and based on historical precedent for comparative insulin studies in which a 0.3% non-inferiority margin is often used.

An exploratory analysis of the percentage of patients with treatment-emergent AIAs (AIA incidence) will be performed to compare the immunogenicity of SAR341402 versus NovoLog/NovoRapid. The sample size of 580 patients would ensure that the 2-sided 90% CI for the adjusted risk difference between SAR341402 and NovoLog/NovoRapid would be included within the [-10%; 10%] interval with at least 68% power. This calculation assumes a true risk difference between the treatment groups of zero and a maximum AIA incidence of 30% (in previous Sanofi clinical studies performed with rapid-acting insulin analogs, AIA incidence in the range of 15-20% were observed at 6 months). The power calculations are presented in Table 1 below.

Table 1 - Power	calculation based	d on the percenta	ge of patients with	treatment-emergent AIAs
			3	

Percentage of patients with treatment-emergent AIAs	10%	20%	30%
Power for N=580 (290/arm)	97%	82%	68%

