2.1.4.7 Immunogenicity variables

If a patient discontinues the treatment prematurely, the process described in Section 2.5.3 will be applied to retrieve immunogenicity assessments performed at the end of treatment visit (Visit 8000).

AIA assessments will be determined in a blinded fashion at a central laboratory (see study flowchart in Appendix A) using a validated anti-insulin antibody binding assay methodology. Only samples collected at least 8 hours after the last administration of mealtime insulin will be taken into account in the analysis.

Anti-insulin antibodies evaluation will consist of:

- Anti-SAR341402/ NovoLog/NovoRapid antibody positive/negative status
- Anti-SAR341402/ NovoLog/NovoRapid antibody titer
- Cross-reactivity to human insulin positive/negative status

The following definitions will be used to identify patients with a change in AIA response during the on-treatment period (see Section 2.1.4 [4]):

- Patients with treatment-induced AIAs will be defined as patients with AIAs that developed de novo (seroconversion) following the IMP administration (ie, patients with at least one positive AIA sample at any time during the on-treatment period, in those patients without pre-existing AIA or with missing sample at baseline).
- Patients with treatment-boosted AIAs will be defined as patients AIA positive at baseline that were boosted to a significant higher titer following the IMP administration (ie, patients with at least one AIA sample with at least a 4-fold increase in titers compared to baseline value at any time during the on-treatment period, in those patients with preexisting AIA). The 4-fold increase in titer corresponds to an increase of two dilution steps within the titration experiment. A single dilution difference (2-fold titer increase) is within the expected imprecision of the titration method and is therefore not considered a relevant change.

Patients with treatment-emergent AIA (Yes, No, Inconclusive) will be derived as follows:

- Patients with treatment-emergent AIAs (AIA incidence) will be defined as patients with treatment-induced or treatment-boosted AIAs.
- Patients without treatment-emergent AIAs will be defined as patients without treatment induced or treatment-boosted AIAs.
- Inconclusive patients will be defined as patients who cannot irrefutably be classified as patients without treatment-emergent AIAs. Inconclusive patients will not be included in the above categories and will be listed separately.

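### The exploratory treatment-emergent AIA risk difference is not adjusted for baseline AIA status, which decides each patient's event rule; the cost is some precision and exposure to chance imbalance, not bias

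*SAP*

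**What the plan says.** **Event definition (SAP 2.1.4.7; protocol 9.2.1.3).** Treatment-emergent AIA combines two rules. A patient who is AIA-negative at baseline, or whose baseline sample is missing, has the event with any positive on-treatment sample. A baseline-positive patient needs "at least a 4-fold increase in titers compared to baseline value at any time during the on-treatment period, in those patients with preexisting AIA".

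**Model (SAP 2.4.5.7; protocol 11.4.4).** The risk difference and its 2-sided 90% CI come from a binomial regression with identity link. On the terms: "The model will include fixed categorical effects for treatment, the randomization strata of geographical region and type of diabetes"; screening HbA1c category and prior NovoLog/NovoRapid use complete the list. The companion logistic model for the same endpoint has the same terms. The SAP says what to do if the logistic model fails to converge, but gives no such rule for the identity-link model.

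**Baseline AIA status.** It is sampled at Visit 3, before treatment (protocol 9.2.1.2), and is not a randomization stratum (SAP 1.1). For AIA incidence it is used only as one entry in the exploratory subgroup list in SAP 2.4.5.7: "Anti-SAR341402/NovoLog/NovoRapid antibody status at baseline (Positive, Negative").

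**Planning (SAP 1.3).** "The sample size of 580 patients would ensure that the 2-sided 90% CI for the adjusted risk difference" between the arms "would be included within the [-10%; 10%] interval with at least 68% power". The assumptions are a true difference of zero and an incidence of at most 30%; on earlier experience, "AIA incidence in the range of 15-20% were observed at 6 months". The power table gives 97%, 82% and 68% at incidences of 10%, 20% and 30% with 290 patients per arm. The analysis is labelled exploratory, with no formal test.

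**The concern.** Baseline status selects the event rule, so it is a prognostic factor by construction unless the rate of induced AIA in negatives happens to equal the rate of boosted AIA in positives. All patients have used insulin for at least a year (protocol exclusion E 03), so pre-existing antibodies cannot be assumed rare. Because randomization is not stratified on this factor, the arms can differ on it by chance, and the planned model does not correct for that.

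This is the one AIA comparison with a power table. SAP 1.5 records that it was added on FDA recommendation and that the increase from 500 to 580 patients was partly meant to give it reasonable power. Using a baseline measurement that is already collected may narrow its interval without recruiting anyone.

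**Working it through.** **1. Reproduce the plan's power.** Inputs from SAP 1.3: 290 per arm, true difference 0, 90% CI within ±10 points. With SE = √(2V/290) and V = p(1−p),

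power = 2Φ(0.10/SE − 1.645) − 1.

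| Incidence p | Recomputed | SAP 1.3 |
|---|---|---|
| 10% | 98.2% | 97% |
| 20% | 82.8% | 82% |
| 30% | 67.4% | 68% |

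The stated figures reproduce to within about 1 point using no covariates at all.

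**2. Effect of adjusting for baseline status.** Let q be the share baseline-positive, p0 the induced rate in negatives and p1 the boosted rate in positives. The documents give none of these, so all values below are assumptions. Overall p = (1−q)p0 + q·p1. After adjustment,

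V = (1−q)p0(1−p0) + q·p1(1−p1),

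which is smaller than p(1−p) by q(1−q)(p0−p1)².

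| q; p0/p1 | p | V before | V after | Fall in V | Power before | Power after |
|---|---|---|---|---|---|---|
| 40%; 40%/15% | 30% | 0.2100 | 0.1950 | 7.1% | 67.4% | 72.1% |
| 50%; 35%/5% | 20% | 0.1600 | 0.1375 | 14.1% | 82.8% | 89.1% |
| 40%; 25%/15% | 21% | 0.1659 | 0.1635 | 1.4% | 81.0% | 81.7% |

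First row in full: V before = 0.30 × 0.70 = 0.2100; V after = 0.6 × 0.24 + 0.4 × 0.1275 = 0.1950. SE goes from √(0.42/290) = 0.0381 to √(0.39/290) = 0.0367.

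Over a wider assumed range (q 20–50%, p1/p0 from 1 down to 0.1), power goes from 67% to 67–86% at 30% incidence and from 83% to 83–90% at 20%. With p0 = p1 the gain is zero.

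**3. Chance imbalance.** The SD of the between-arm difference in baseline positivity is √(2q(1−q)/290). For q = 40% this is √(0.48/290) = 4.1 points. Multiplied by p0 − p1 = 0.25, a 1-SD imbalance shifts the unadjusted difference by about 1.0 point, and a 1.96-SD imbalance (8.0 points) by about 2.0. For q = 50% and p0 − p1 = 0.30, 1.96 SD is 8.1 points and the shift is about 2.4.

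**4. Validity of the planned estimate.** In 20,000 simulated trials per scenario at zero true difference, the unadjusted estimate averaged 0.000 and its 90% CI covered 89–91%.

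**5. Can the planned model carry the extra term?** The additive identity-link model was simulated in the three scenarios above with 580 patients. Assumed: Europe T1DM/US T1DM/US T2DM/Japan T1DM shares of 36/40/17/7%, the other strata split 50/50, and no stratum or treatment effects. With baseline status added, the maximum-likelihood fit had a fitted risk of zero in about 10%, 79% and 8% of trials, in table order. Without it the figure was 0–1.5%. On the boundary the usual Wald interval is unreliable.

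**The case against.** **The gain is assumed and may be nil.** This stands. No document gives baseline positivity or separate induced and boosted rates. The calculation also starts from a model without covariates. The planned model already holds prior NovoLog/NovoRapid use, which may carry part of the baseline status, so the gain over that model could be smaller than the table shows.

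**The 68% is the worst case.** Also fair. At the expected incidence of 15–20% the same formula gives about 92% and 83%. A 1.96-SD imbalance is a 1-in-20 event; 1 SD is the more typical size.

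**Adding one term can break the model.** This stands, and it changes the remedy. The scenario with the largest gain is the one in which the additive identity-link fit usually reaches its boundary.

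**The plan already shows baseline status.** Induced and boosted counts are tabulated separately, and AIA results are displayed by baseline status. These would reveal an imbalance but do not adjust the overall difference. SAP 2.4.5.7 also omits the baseline-factor subgroups from the separate T1DM analyses, which concern about 480 of the 580 patients.

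**Stronger readings the documents do not support.**
- A reader might infer that the planned difference is biased or its interval invalid. Randomization protects both, as step 4 shows.
- A reader might infer that the sample size is wrong. The power figures reproduce and do not depend on the omitted term.
- A reader might infer that screening HbA1c should make way for baseline AIA status. It is a randomization stratum, and nothing requires dropping it.
- A reader might infer that baseline status is known for everyone. SAP 2.1.4.7 provides for a missing baseline sample and excludes samples taken less than 8 hours after mealtime insulin.

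**Conclusion.** The omission is real and worth correcting, as an efficiency point on an exploratory comparison. Baseline AIA status determines the event rule, is measured before treatment, and is absent from both models of AIA incidence. The planned risk difference remains unbiased with valid coverage.

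Under the assumed rates, the chance of the 90% CI lying within ±10 points rises by about 5 points (67% to 72%) or 6 points (83% to 89%), by under 1 point when the risks are close, and by nothing when they are equal. These figures rest on 290 evaluable patients per arm, a true difference of zero, a normal approximation, and values of q, p0 and p1 that the documents do not supply. The direction follows from the event definition; the size cannot be fixed from the plan.

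**What to change.** In SAP 2.4.5.7 and protocol 11.4.4:

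1. Adjust the AIA risk difference and its 90% CI for baseline AIA status, positive versus negative, with missing grouped with negative as the event definition already does.
2. Keep all randomization strata, including screening HbA1c.
3. Do not rely on the additive identity-link fit alone. Obtain the estimate from a standardized risk difference based on the logistic model, or from a Mantel-Haenszel-type risk difference stratified by baseline AIA status, or name one of these as the fallback if the identity-link fit fails or reaches its boundary. The standardized version carries all the strata as covariates. A Mantel-Haenszel estimate stratified by baseline status alone does not, so it suits the fallback role better.
4. Add the same term to the companion logistic model, so that both analyses of the endpoint use the same adjustment.

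The cost is a little extra programming and one more model term. No new data are needed, and the marginal risk difference remains the target. Under protocol 8.3.1, treatment allocation enters the study database only at the 6-month lock, so the change should be specified before then.
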